## 2.5 | Statistical analysis

Although no studies employing this technique were found in the literature, from a study on direct and indirect techniques in CIIC22 we expected a mean difference of 1 mm. A statistical power analysis was performed to determine the number of patients with an equivalence study design. With an  $\alpha = .05$ , and a power of 0.80, the calculations revealed that at least six patients would be needed to be 95% sure that the limits of a two-sided 90% confidence interval would exclude a difference in means of more than 500  $\mu\text{m}$ .

Primary outcomes were defined as the variation in the RMS between the two methods in the hard (teeth) and soft (teeth and periimplant mucosa) tissues' measurements. Descriptive statistic (means and 95% confidence intervals) was performed on the studied parameters. Normality of distribution was tested by the Shapiro-Wilk Normality test and the Levene test was used to assess the equality of variance. According to the results, the nonparametric Mann-Whitney U and Kruskal-Wallis tests were used to compare RMS between methods in hard and soft tissues ( $\alpha = .05$ ). When performing multiple comparisons, the P-value was adjusted according to the Bonferroni Correction method.

Effect size between soft tissues' measurements (tooth vs implants) was calculated as Hedges'  $g$   $\pm$  95% confidence interval as a result of different sample sizes. Effect size was considered as small (<0.3), moderate (0.3–0.8), or large ( $\geq 0.8$ ) effect. The level of significance was set at .05. All calculations were carried out with statistical software (SPSS 25.0, SPSS Inc., Chicago, Illinois).

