## 2.4 | 3D analysis

Two STL files were obtained from each patient and, to allow for blinding, an external operator provided the STL files named with the patient reference number followed by the letter A (reference) or B (measured), keeping the correspondence code in an opaque sealed envelope until the end of the study. The files were imported into a reverse engineering software Geomagic Design X (3D Systems, Rock Hill, South Carolina) where they were cut to the zone of interest with the “Split” tool, removing unnecessary information and submitted to the “Healing Wizard” to reduce the number of distortions and small artifacts that could influence analysis. The generated datasets were then imported into the point-cloud inspection software Geomagic Control X (3D Systems).

Software validation was performed as previously reported and repeated five times per scan (60 repetitions in total) to check software reliability, after which, virtual sagittal planes were created to guide the standardization of the locations of interest—through the cervicalapical axis of each of the five structures (four teeth and one implant), frontal planes over the mesiodistal axis of the implant and the two adjacent teeth, three transversal planes parallel between them in the four teeth, one at the gingival zenith and two others apically from the first with 1 mm spacing between them, and in the implant at emergence profile base level which was defined with a horizontal plane in the most apical identifiable point of the customized emergence profile, mucosal zenith, and in the middle of them. The locations were determined by the intersection between the described planes with the superimposed scans and the linear differences obtained by the 3D analysis program. The amount of deviation between methods was obtained by calculating the root mean square (RMS) by previously established methods.

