To evaluate the trueness between conventional (reference) and digital (comparison) impression methods, RMS distances were determined on both the buccal and palatal sides of the teeth, at cervical, incisal and in the middle point between them in each tooth (Bc, Bm, Bi, Pc, Pm, and Pi) and in the respective soft tissues (Gbc, Gbm, Gbz, Gpz, Gpm, and Gpc), as shown in Figure 4A. In the interproximal area of the implant (mesial and distal sides, Mip and Dip), the same locations as in buccal/palatal were measured (Figure 4B). In total, 304 comparisons were performed in teeth's hard and soft tissues to assess trueness between methods.

To evaluate the soft tissue replication between methods in periimplant soft tissues, the locations were measured at emergence profile base level (epbl), at the zenith (z), and middle (m) on the different sides of the implant mucosa: the buccal of the buccal mucosa (Bbm), the palatine of the buccal mucosa (Pbm), the buccal of the palatine mucosa (Bpm), the palatine of the palatine mucosa (Ppm), and the mesial and distal mucosa (Mm and Dm, respectively) (Figure 4C,D), corresponding to 18 locations per patient, amounting to a total of 108

measurements. If the scans presented teeth with modifications, for prosthesis fabrication or distortions, the affected areas were not assessed.

For each location with the “3D Compare” tool an area of interest with at least 1 mm^2 was selected and used to measure the differences between methods, with three replicates performed per location. The analysis software automatically calculated RMS and the mean of the three replicates considered for statistical analysis.

For optimal 3D visualization, a colored map was created with negative (blue, showing the comparison scan going inwards) and positive values (red, going outwards), as shown in Figure 5. Specific parameters were set to the color scale, ranging from +1000 to -1000  $\mu\text{m}$  and the best results ranging between +100 and -100  $\mu\text{m}$ , highlighted in green. Values over or below the color scale's limits were presented in gray.

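### The case for six patients cannot be reproduced: a 1 mm expected difference against a 500 µm margin, two values for one power, and no SD

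*Combined protocol and SAP*

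**What the plan says.** The sample size is justified in two sentences of section 2.5 (Statistical analysis).

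- The authors found no study of this technique. From a study comparing direct and indirect coping techniques, "we expected a mean difference of 1 mm".
- For an equivalence design with α = .05 "and a power of 0.80", the plan concludes: "at least six patients would be needed to be 95% sure that the limits of a two-sided 90% confidence interval would exclude a difference". The margin is 500 µm.

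No SD is given anywhere in the document. Apart from the 1 mm, no assumed true difference is given. The text does not say whether a paired or a two-group formula was used.

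On the outcome, section 2.5 states: "Primary outcomes were defined as the variation in the RMS between the two methods". Section 2.4 (3D analysis) uses RMS as the measure of deviation between the two scans. It also gives the peri-implant measurement count as "corresponding to 18 locations per patient, amounting to a total of 108" measurements, and 108/18 = 6 patients.

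**The concern.** Four things in this short paragraph stand out.

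1. The only difference mentioned, 1 mm, is twice the 500 µm margin. An equivalence study cannot be expected to succeed when the anticipated difference lies outside the margin. The text does not say what part the 1 mm played.
2. In an equivalence design, the probability that both limits of the 90% interval fall inside the margin is the power. One sentence gives it as 0.80 and as 95%.
3. The sample size depends directly on the SD and on the assumed true difference. Neither is available in usable form.
4. An RMS deviation cannot be negative, whereas a two-sided ±500 µm criterion belongs to signed differences. The scale of the calculation is not stated.

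This paragraph is the only support for studying six patients under an equivalence label. A reader would take from it an 80% or 95% chance of showing equivalence within 500 µm.

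**Working it through.** **Inputs from section 2.5.** α = .05 (a two-sided 90% interval, that is, two one-sided tests at 5% each); power 0.80 or 0.95; margin 0.5 mm; expected difference 1 mm; n = 6. Both impressions come from the same patient (section 2.4), so the paired calculation is the natural one. Every SD below is an assumption, because the document gives none. Differences are taken as signed and normally distributed.

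**Can six be reproduced?** Not from the stated inputs. With a true difference of 0, the normal approximation for paired data is

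n = [SD × (z₀.₉₅ + z₁₋β/₂) / 0.5]².

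- 80% power: 1.645 + 1.282 = 2.926 (from unrounded values). Then n = 6 when the SD is above 0.5 × √5 / 2.926 = 0.382 mm and at most 0.5 × √6 / 2.926 = 0.419 mm.
- 95% power: 1.645 + 1.960 = 3.605. Then n = 6 when the SD is above 0.310 and at most 0.340 mm.

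The two ranges are disjoint. For a given SD, 95% needs (3.605/2.926)² = 1.52 times the sample that 80% needs.

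**Exact calculation.** At n = 6 the approximation is rough, so power was also computed as

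P(|mean| + t₀.₉₅,ₙ₋₁ × s/√n < 0.5),

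integrating over the distribution of the sample SD s. The SD ranges (mm) for which six is the smallest adequate n are:

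| True difference (mm) | 80% power | 95% power |
|---|---|---|
| 0 | 0.312–0.358 | 0.250–0.288 |
| 0.1 | 0.287–0.329 | 0.219–0.253 |
| 0.2 | 0.221–0.253 | 0.165–0.190 |
| 0.25 | 0.184–0.211 | 0.137–0.158 |
| 0.3 | 0.147–0.169 | 0.110–0.127 |
| 0.4 | 0.074–0.084 | 0.055–0.063 |

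No row overlaps. With no true difference and SD 0.358 mm, power is 65.7% at n = 5, 80.0% at 6, 94.1% at 8 and 96.9% at 9, so 95% needs nine patients. At SD 0.288 mm, six give 95.0%, but five already give 86.9%, so six is not the minimum for 80%.

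**Independent groups, six per method, no true difference.** 80% needs an SD of at most 0.275 mm, at which 95% takes nine per method (95.9%). 95% needs an SD of at most 0.223 mm, at which five per method already give 88.6%. The conflict is the same.

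**If 1 mm was the planning difference.** The test passes at most 5% of the time when the true difference equals the margin, and no more often beyond it. Power therefore cannot exceed 5% at any n. For six pairs the maximum over all SDs is 0.145%, at an SD of about 1.02 mm.

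**If 1 mm was the SD.** With no true difference, 80% needs 36 pairs (80.5%; 35 give 79.0%) and 95% needs 54 pairs (95.3%; 53 give 94.8%).

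**If the scale is RMS.** Only the upper limit is then compared with 0.5 mm. With a mean of 1 mm and n = 6, the chance of success is 0.01% at SD 0.5 mm and 0.3% at SD 1.0 mm.

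**The case against.** The strongest reply is that six has not been shown to be wrong, and that is true: the table lists inputs that give it. What is shown is contradictory and incomplete reporting, not a proven miscalculation.

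The 1 mm may also be background, or the source of a margin set at half its size. It comes from a different comparison, and the sentence that makes the calculation does not use it. The near-zero power therefore holds only if 1 mm was the planning difference. If it was not, the planning difference is missing.

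The 95% may be a slip prompted by α = .05 and the 90% interval, since power is explicitly labelled 0.80. One changed phrase would then settle that part. As printed, however, the sentence attaches 95% to the event that defines power.

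The SD may be in the cited source, so the fair statement is that it is absent from this document. The outcome might also mean a difference between RMS values, which can be negative; on this point the text is ambiguous rather than wrong. The SD ranges above assume normal signed differences and may not describe the outcome analysed.

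Finally, the document is written in the past tense, and its analysis section plans 95% intervals, Mann-Whitney U and Kruskal-Wallis tests. None of these applies the 90% interval against 500 µm. This lowers the practical weight of the power statement but does not make it correct.

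**Conclusion.** The concern holds. As written, section 2.5 gives two incompatible values for one power. At every true difference examined from 0 to 0.4 mm, no single SD makes six the minimum for both. The paragraph also sets an expected difference of twice the margin beside an equivalence claim without reconciling them, and it omits the SD on which the sample size depends.

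How much of the assurance survives turns on inputs that only the authors can supply. With no true difference and paired analysis, 80% requires an SD of at most 0.358 mm and 95% an SD of at most 0.288 mm. With a true difference of 1 mm, neither figure is attainable at any sample size.

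The contradiction over power follows from the wording together with the exact calculation. The 1 mm result is conditional on the role of that figure. The missing SD and scale taken alone would be gaps in reporting. The paragraph needs correcting before it is cited in support of an equivalence conclusion.

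**What to change.** Keep n = 6 and rewrite the paragraph from the inputs actually used, for example:

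*Six patients were calculated assuming a true mean [signed or RMS] difference of [value used] and an SD of within-patient differences of [value used], giving [one value]% power for the two-sided 90% confidence interval to lie within the 500 µm margin.*

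- State one power value and delete the other.
- Say whether the formula was paired or two-group. If it was two-group, define the SD accordingly.
- Say what the 1 mm was used for, or remove it.
- If the scale is RMS, say that only the upper confidence limit is compared with 500 µm.
- If 1 mm was the planning difference, or the inputs cannot be recovered, withdraw both power figures, say why, and state that six patients were not shown to have adequate power for equivalence within 500 µm.
- Do not pick an SD afterwards to fit six.

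The cost is one paragraph of text. No patients are added, and no measurements or tests change. The drawback is that the stated assurance becomes weaker or disappears, so any equivalence conclusion loses its power support.

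### The study is sized for equivalence within 500 µm on several primary tissue outcomes, but the planned difference tests with Bonferroni adjustment test agreement on none of them and do not limit false agreement across them

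*Combined protocol and SAP*

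**What the plan says.** All of the decision material is in section 2.5 of the combined protocol and SAP.

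- **Objective and size.** "A statistical power analysis was performed to determine the number of patients with an equivalence study design". The criterion is "to be 95% sure that the limits of a two-sided 90% confidence interval would exclude a difference in means of more than 500" µm, with alpha .05 "and a power of 0.80", giving "at least six patients would be needed". The same paragraph gives an expected mean difference of 1 mm.
- **Primary outcomes.** "Primary outcomes were defined as the variation in the RMS between the two methods in the hard (teeth) and soft (teeth and periimplant mucosa) tissues'". This is a plural definition. It can be read as two outcomes (hard, soft) or three (tooth hard tissue, tooth soft tissue, peri-implant mucosa).
- **Inference.** Means with 95% confidence intervals are descriptive. Mann-Whitney and Kruskal-Wallis tests are run at .05, and "When performing multiple comparisons, the P-value was adjusted according to the Bonferroni Correction method". The family and the number of comparisons are not given.
- **Measurements.** Section 2.4 gives 304 comparisons on teeth. For the peri-implant mucosa it describes a set "corresponding to 18 locations per patient, amounting to a total of 108" measurements.

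After the sample-size sentence, neither the 500 µm limit nor the 90% interval appears again.

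**The concern.** The sample-size paragraph and the analysis paragraph answer different questions. The first asks whether the two impression methods agree within 500 µm. The second asks whether distributions of RMS differ. A significant rank test does not show that 500 µm is exceeded, and a non-significant one does not show that it is respected. Followed as written, the plan yields no result on a primary outcome that supports or refutes equivalence at the stated limit.

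Several primary outcomes make this worse. They could give opposite answers: tooth surfaces might agree closely while the peri-implant mucosa does not. The plan does not say which outcome decides, or whether one, any or all must meet the limit. Bonferroni on difference tests limits false findings of difference. The error that matters for an equivalence claim is declaring agreement when a tissue exceeds the limit, and nothing in section 2.5 limits that error.

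**Working it through.** **1. The plan's own figure.** Inputs from section 2.5: one-sided alpha .05 (the 90% interval), power 0.80, limit 500 µm, n = 6. No SD is given, so six patients can be neither confirmed nor refuted. The usual normal approximation, taking a true difference of zero, is

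n = [SD × (z₀.₉₅ + z₀.₉₀) / 500]² for paired differences, and twice that per arm for two samples.

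Solving for SD at n = 6:
- paired: SD = 500 × √6 / (1.645 + 1.282) ≈ 419 µm
- six per arm: SD = 500 × √3 / 2.926 ≈ 296 µm
- paired, with the 95% in that sentence read as power: SD = 500 × √6 / (1.645 + 1.960) ≈ 340 µm

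These SDs are implied, not stated. If the 1 mm expected difference were the true value, no sample size would work, because it is twice the limit; simulated power at n = 6 is essentially zero.

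**2. What the planned analysis delivers**

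| Needed for the equivalence aim | In the analysis paragraph |
|---|---|
| 90% interval compared with 500 µm | 95% interval, descriptive, no limit attached |
| Test against the limit | Rank tests of difference at .05 |
| Rule across primary outcomes | None |
| Control of false agreement | None; Bonferroni applies to difference P-values |

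**3. Illustrative size if any one outcome sufficed.** Assumptions: each of k outcomes is assessed at one-sided .05, n = 6, and every true mean lies exactly at 500 µm.

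Independent outcomes: 1 − 0.95² = 0.0975 and 1 − 0.95³ = 0.143.

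Correlated outcomes, by simulation of one-sample t tests:

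| Correlation | k = 2 | k = 3 |
|---|---|---|
| 0 | 0.097 | 0.143 |
| 0.5 | 0.089 | 0.124 |
| 0.8 | 0.079 | 0.100 |

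**4. If all outcomes had to agree.** Overall equivalence is then false whenever at least one outcome is at or beyond the limit. That outcome passes with probability at most .05, so the overall error is at most .05 without any adjustment.

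**5. Cost of the all-outcomes rule.** With power 0.80 for each outcome and independence, joint power is 0.80² = 0.64 or 0.80³ = 0.512. Positive correlation raises both. To restore 0.80 jointly, each outcome needs 0.80^(1/2) = 0.894 or 0.80^(1/3) = 0.928. At an assumed paired SD of 418 µm, the formula in step 1 then gives:
- k = 2: [418 × (1.645 + 1.618) / 500]² = 7.4, so 8 patients
- k = 3: [418 × (1.645 + 1.802) / 500]² = 8.3, so 9 patients

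These are optimistic. At n = 6 and SD 418 µm, a t-based 90% interval has simulated power of about 0.62 for a single outcome, not 0.80, even at a true difference of zero.

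**The case against.** Three stronger readings are tempting. The documents support none of them.

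**That Bonferroni pushes the study towards agreement.** A reader might infer that each added comparison makes a favourable conclusion easier. Section 2.4 defines RMS as the deviation between the two methods, so each location yields one deviation and not one value per method. Rank tests on such values may therefore only compare tissues, sides or levels; the tooth-versus-implant effect size in section 2.5 fits that reading. For those questions Bonferroni runs in its conventional direction. Section 2.5 does describe the tests as comparing methods, so the wording is unclear, but nowhere does it say that non-significance will be read as agreement. What stands is narrower: on either reading, these tests do not address the 500 µm limit.

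**That the plan carries a 10–14% false-agreement rate.** Those figures need a rule that any one outcome suffices, and the plan states no such rule. They also put every true mean exactly at the limit. Three outcomes is an interpretation, and two is as literal a reading. The figures show what the silence permits, not what the plan does.

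**That site comparisons can never reach significance after adjustment.** This would need only six values per group. Section 2.4 gives 18 locations on six sides, so three levels per side and 3 × 6 = 18 values per side over six patients. Larger groups are likely, though values from one patient are not independent. Pairwise testing of single locations is not stated.

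It is also fair to say that the missing equivalence test is the root defect and multiplicity is secondary. That stands. But adding a 500 µm test without a rule across tissue groups would still leave the deciding outcome open.

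**Conclusion.** The point holds in this form: the study is sized for equivalence, several tissue outcomes are primary, and the planned inference neither tests agreement within 500 µm on any of them nor limits false agreement across them. This follows from the text of section 2.5 and does not depend on a simulation.

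The size is conditional. The choice between requiring any one outcome and requiring all moves the worst-case false-agreement rate from about 0.08–0.10 (two outcomes) or 0.10–0.14 (three) to at most .05. This assumes one value per patient per outcome, n = 6, one-sided .05 and approximately normal patient-level values.

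The conflict between 500 µm and 1 mm cannot be resolved from the documents. They do not say whether 1 mm entered the calculation as the assumed true difference, so it should not be inferred that the study could not succeed.

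**What to change.** In section 2.5, replace the primary-outcome and Bonferroni sentences with a decision rule along these lines:

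> The primary tissue groups are tooth hard tissue, tooth soft tissue and peri-implant mucosa. For each group, the between-method deviation is summarised as one value per patient. The methods are declared equivalent only if, in every group, the 90% confidence interval for the mean deviation lies within 500 µm. Because all groups must meet the limit, each is tested at one-sided .05 with no alpha split.

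If the sponsor intends two groups, name two. RMS cannot be negative, so in practice the upper confidence limit decides.

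Then:
- Label rank tests between tissues, sides, levels and locations exploratory. Apply Bonferroni only there, state the number of comparisons, and state that a non-significant P-value is not evidence of agreement.
- State the SD and true difference behind the six patients, and reconcile the 500 µm limit with the 1 mm expectation and the 0.80 power with the 95% in the same sentence.
- State that the 0.80 power applies to each outcome, and that joint power may be as low as about 0.64 (two) or 0.51 (three).

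**Cost.** The changes are to wording and need no new data. Overall equivalence becomes materially harder to claim with six patients, and location-level results lose confirmatory standing. Keeping joint power at 0.80 would take about 8 or 9 patients under the assumptions in the working, and more with a t-based interval. The text is written in the past tense; if results have already been seen, a rule adopted now should be reported as post hoc.

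### The study is sized to show equivalence within 500 µm, but no analysis compares the between-method deviation with 500 µm, and the named tests can only compare tissues or sites.

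*Combined protocol and SAP*

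**What the plan says.** Section 2.5 of the combined protocol and SAP opens with the sample size: "A statistical power analysis was performed to determine the number of patients with an equivalence study design". With alpha .05 and power 0.80, six patients are said to suffice so that "the limits of a two-sided 90% confidence interval would exclude a difference in means of more than 500" µm.

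The same section makes the between-method RMS in hard and soft tissues the primary outcome. Its analyses are:

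- "Descriptive statistic (means and 95% confidence intervals) was performed on the studied parameters";
- Shapiro-Wilk and Levene checks, after which "the nonparametric Mann-Whitney U and Kruskal-Wallis tests were used to compare RMS between methods in hard and soft tissues", with Bonferroni adjustment for multiple comparisons;
- Hedges' g for soft tissue, tooth against implant.

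Section 2.4 defines the data. "The amount of deviation between methods was obtained by calculating the root mean square (RMS) by previously established methods". The conventional model is the reference and the digital scan is the comparison. There is one value per location: "The analysis software automatically calculated RMS and the mean of the three replicates considered for statistical analysis". For the peri-implant mucosa the locations are described as "corresponding to 18 locations per patient, amounting to a total of 108" measurements.

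**The concern.** An equivalence claim needs an interval, or two one-sided tests, set against the margin. After the sample size sentence the document mentions neither 500 µm nor a 90% interval. The only tests named have a null hypothesis of no difference, and failing to reject that null is not evidence of equivalence.

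The tests also do not fit the data. Each RMS value is already a digital-versus-conventional deviation, and the reference method has no RMS of its own. A comparison of RMS between methods therefore has no two groups to compare. The available groups are tissues or sites.

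At stake is the main conclusion. A non-significant P could be reported as agreement between methods when both tissues deviate far beyond the margin. A significant P could be reported as disagreement when both lie well inside it.

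**Working it through.** **1. The plan's own figure.** The document gives no SD, so six patients cannot be reproduced, only back-solved. For a paired comparison with true difference 0, n = SD² × (z₀.₉₅ + z₁₋β/₂)² / 500². With n = 6 and power 0.80, SD = 500 × 2.449 / (1.645 + 1.282) = 418 µm. The t-based version gives about 358 µm. Six is attainable under some SDs. The point here is what is done with the margin afterwards.

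**2. Can the named analyses register 500 µm?** Mann-Whitney U and Kruskal-Wallis depend only on ranks. Hedges' g depends only on a difference in means and a pooled SD. Adding a constant to every RMS value changes none of these. A numerical check with shifts of 0, 500, 1000 and 5000 µm gave identical P values, and g agreed to rounding error. This holds for any data set and needs no assumption.

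An illustration with assumed values, six RMS values per tissue:

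| True mean RMS, tissue 1 / tissue 2 (µm) | SD (µm) | Mann-Whitney rejects |
|---|---|---|
| 100 / 100 (both inside the margin) | 60 | about 4% |
| 800 / 800 (both outside) | 60 | about 4% |
| 50 / 200 (both inside) | 40 | about 100% |
| 800 / 950 (both outside) | 40 | about 100% |

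The result is the same on either side of the margin.

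**3. What a margin-based analysis would need with six patients.** The half-width of the patient-level 90% interval is t(0.95, 5 df) / √6 × SD = 2.015 / 2.449 × SD = 0.823 SD, where SD is that of the patient means. The upper limit is below 500 µm only if SD < (500 − observed mean) / 0.823:

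- observed mean 200 µm: SD under 365 µm;
- observed mean 300 µm: SD under 243 µm;
- observed mean 400 µm: SD under 122 µm.

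**4. Does the descriptive 95% interval fill the gap?** Only if it is computed per patient and read against 500 µm. The document says neither, and Section 2.4 carries location values into the analysis (6 × 18 = 108 for the mucosa). The documents give no intraclass correlation (ICC), so the following is illustration. Suppose the true mean RMS is exactly 500 µm. The table shows how often the upper limit falls below 500 µm, by simulation with 100,000 studies per setting and normal data:

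| ICC | 95% CI over 108 locations as independent (nominal 2.5%) | Patient-level 90% CI (nominal 5%) |
|---|---|---|
| 0.1 | 11.6% | 4.9% |
| 0.3 | 21.9% | 5.1% |
| 0.5 | 27.3% | 5.0% |

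The design effect agrees roughly. With 1 + 17 × ICC = 2.7, 6.1 and 9.5, the normal approximation Φ(−1.982 / √design effect) gives 11%, 21% and 26%. With right-skewed data (lognormal, CV 0.5 to 0.8, same ICCs on the log scale) the location-level rates are 14% to 33% and the patient-level rates 7% to 12%.

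**The case against.** The strongest reply is that means with 95% intervals are specified, and a reader can hold their upper limits against 500 µm. That is true. But the document does not state this reading, does not say whether patient or location is the unit, and uses a different level from the one used for sizing. It leaves the answer to the reader.

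Second, the margin was set for a difference in means, whereas RMS is non-negative and mixes bias with scatter. This stands as a point of interpretation. It does not undermine the remedy, because RMS is at least as large as the absolute mean deviation. A mean RMS below 500 µm therefore implies a mean signed difference within ±500 µm. The rule is conservative for the signed reading, and failing it would not show that the signed difference exceeds the margin.

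Third, the t interval is liberal for skewed RMS with six patients, at 7% to 12% against a nominal 5% in the lognormal runs. This stands. A patient-level 95% interval gave about 4% to 8% in the same settings, at the price of a wider half-width (1.049 SD). The 90% level matches the sizing statement.

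Fourth, the ICC figures rest on assumed inputs, and nothing in the text says that locations are pooled as independent. Agreed. They show why the unit must be stated, and the main defect does not depend on them.

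Fifth, tissue or site comparisons may be a legitimate question. They may, but it is not the question that set the sample size.

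Last, the document is written in the past tense, so any rule added now comes after data collection. That is correct and must be disclosed.

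**Conclusion.** The concern holds and must be fixed. Followed exactly, the plan gives no valid answer to the question that determined its sample size. The named tests and the effect size are unaffected by whether the digital scan deviates by a little or by far more than 500 µm. That result follows from the definitions in Sections 2.4 and 2.5 and needs no assumed SD or ICC.

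The plan's descriptive interval could supply the answer, but only at patient level and read against the margin. If it were taken over locations as independent, false equivalence at the margin would be roughly 12% to 27% for ICCs of 0.1 to 0.5 with normal data. Those rates depend on the assumed ICC and on the distribution.

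**What to change.** Replace the inferential text in Section 2.5 as follows.

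- For each primary outcome (tooth hard tissue, tooth soft tissue, peri-implant mucosa), average RMS within patient. Report the mean over patients with its two-sided 90% interval (t, n − 1 df).
- Conclude equivalence for an outcome only if the upper limit, which is the one-sided 95% bound, is below 500 µm. Use the ±500 µm form only if signed deviations are available. Each outcome is concluded separately. A single overall claim would need all three to pass.
- Show the individual patient means beside each interval, because of the skewness issue with six patients. State how many locations enter each mean, since Section 2.4 allows affected areas to be left unassessed. Report the mucosal levels (base, middle, zenith) descriptively, so that averaging does not hide a large local deviation.
- Keep Mann-Whitney U and Kruskal-Wallis as exploratory tissue or site comparisons. State that a non-significant P is not evidence of equivalence.
- Label the rule as added after data collection.

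The cost is revised wording and three intervals from RMS data already collected. The downside is power: the rule may fail even when the true mean RMS is below 500 µm. For 80% power with six patients (noncentral t, 5 df, noncentrality 2.905), the SD of patient means can be at most (500 − true mean) × 2.449 / 2.905. That is about 253 µm at a true mean RMS of 200 µm and about 84 µm at 400 µm.
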